4.9.1.3. Multiplicity

To control the overall Type I error rate at 0.05 across the primary endpoints and secondary endpoints for the final analysis, the gatekeeping testing strategy will be applied to the primary endpoint family and secondary endpoint family. The hierarchical testing procedure will be utilized within the primary endpoint family and secondary endpoint family.

For the primary endpoint family, the 2 treatment arms will be compared against pooled placebo using the hierarchical testing procedure, in which the ISIS 678354 80 mg treatment group will be compared to the pooled placebo at the 2-sided alpha level of 0.05, if the comparison is statistically significant (p < 0.05), then the ISIS 678354 50-mg treatment group is compared against the pooled placebo at the alpha level of 0.05. If the comparison of the ISIS 678354 80-mg treatment group is not statistically significant, then the comparison of the ISIS 678354 50-mg treatment group against pooled placebo and all secondary endpoints will be considered exploratory.

Testing of secondary endpoint family will be performed only if the comparison of the primary endpoint is statistically significant (p < 0.05) for both ISIS 678354 80-mg and 50-mg treatment groups. Testing of the secondary endpoint family will be conducted according to the following sequence:

- Secondary endpoint 1: comparison of percent change in fasting TG from Baseline to Month 12 between ISIS 678354 80-mg treatment group and pooled placebo in FAS
- Secondary endpoint 2: comparison of percent change in fasting apoC-III from Baseline to the primary analysis time point between ISIS 678354 80-mg treatment group and pooled placebo in FAS
- Secondary endpoint 3: comparison of percent change in fasting apoC-III from Baseline to Month 12 between ISIS 678354 80-mg treatment group and pooled placebo in FAS
- Secondary endpoint 4: comparison of proportion of patients who achieve ≥ 40% reduction in fasting TG from Baseline to the primary analysis time point between ISIS 678354 80-mg treatment group and pooled placebo in FAS
- Secondary endpoint 5: comparison of percent change in fasting apoB-48 from Baseline to the primary analysis time point between ISIS 678354 80-mg treatment group and pooled placebo in FAS
- Secondary endpoint 6: comparison of percent change in fasting non-HDL-C from Baseline to the primary analysis time point between ISIS 678354 80-mg treatment group and pooled placebo in FAS
- Secondary endpoint 7: comparison of percent change in fasting TG from Baseline to Month 12 between ISIS 678354 50-mg treatment group and pooled placebo in FAS
- Secondary endpoint 8: comparison of percent change in fasting apoC-III from Baseline to the primary analysis time point between ISIS 678354 50-mg treatment group and pooled placebo in FAS
- Secondary endpoint 9: comparison of percent change in fasting apoC-III from Baseline to Month 12 between ISIS 678354 50-mg treatment group and pooled placebo in FAS
- Secondary endpoint 10: comparison of proportion of patients who achieve $\geq 40\%$ reduction in fasting TG from Baseline to the primary analysis time point between ISIS 678354 50-mg treatment group and pooled placebo in FAS
- Secondary endpoint 11: comparison of percent change in fasting apoB-48 from Baseline to the primary analysis time point between ISIS 678354 50-mg treatment group and pooled placebo in FAS
- Secondary endpoint 12: comparison of percent change in fasting non-HDL-C from Baseline to the primary analysis time point between ISIS 678354 50-mg treatment group and pooled placebo in FAS
- Secondary endpoint 13: comparison of adjudicated acute pancreatitis event rate from Week 1 to Week 53 between pooled ISIS 678354 treatment group and pooled placebo in the subset of FAS with a prior history of pancreatitis within 10 years prior to Screening
- Secondary endpoint 14: comparison of adjudicated acute pancreatitis event rate from Week 1 to Week 53 between pooled ISIS 678354 treatment group and pooled placebo in FAS
- Secondary endpoint 15: comparison of adjudicated acute pancreatitis event rate from Week 13 to Week 53 between pooled ISIS 678354 treatment group and pooled placebo in the subset of FAS with a prior history of pancreatitis within 10 years prior to Screening

- Secondary endpoint 16: comparison of adjudicated acute pancreatitis event rate from Week 13 to Week 53 between pooled ISIS 678354 treatment group and pooled placebo in the FAS
- Secondary endpoint 17: comparison of proportion of patients who achieve ≥ 70% reduction in fasting TG from Baseline to the primary analysis time point between ISIS 678354 80-mg treatment group and pooled placebo in FAS
- Secondary endpoint 18: comparison of percent change in fasting non-HDL-C from Baseline to Month 12 between ISIS 678354 80-mg treatment group and pooled placebo in FAS
- Secondary endpoint 19: comparison of percent change in fasting apoB-48 from Baseline to Month 12 between ISIS 678354 80-mg treatment group and pooled placebo in FAS
- Secondary endpoint 20: comparison of proportion of patients who achieve fasting $TG \le 880 \text{ mg/dL}$ at the primary analysis time point between ISIS 678354 80-mg treatment group and pooled placebo in the FAS
- Secondary endpoint 21: comparison of proportion of patients who achieve ≥ 70% reduction in fasting TG from Baseline to the primary analysis time point between ISIS 678354 50-mg treatment group and pooled placebo in FAS
- Secondary endpoint 22: comparison of percent change in fasting non-HDL-C from Baseline to Month 12 between ISIS 678354 50-mg treatment group and pooled placebo in FAS
- Secondary endpoint 23: comparison of percent change in fasting apoB-48 from Baseline to Month 12 between ISIS 678354 50-mg treatment group and pooled placebo in FAS
- Secondary endpoint 24: comparison of proportion of patients who achieve fasting $TG \le 880 \text{ mg/dL}$ at the primary analysis time point between ISIS 678354 50-mg treatment group and pooled placebo in the FAS
- Secondary endpoint 25: comparison of adjudicated acute pancreatitis event rate from Week 1 to Week 53 between pooled ISIS 678354 treatment group and pooled placebo in the subset of FAS with ≥ 2 events of adjudicated acute pancreatitis in 5 years prior to enrollment
- Secondary endpoint 26: comparison of adjudicated acute pancreatitis event rate from Week 13 to Week 53 between pooled ISIS 678354 treatment group and pooled placebo in the subset of FAS with ≥ 2 events of adjudicated acute pancreatitis in 5 years prior to enrollment
- Secondary endpoint 27: comparison of proportion of patients who achieve fasting $TG \le 500 \text{ mg/dL}$ at the primary analysis time point between ISIS 678354 80-mg treatment group and pooled placebo in FAS
- Secondary endpoint 28: comparison of proportion of patients who achieve fasting $TG \le 500 \text{ mg/dL}$ at the primary analysis time point between ISIS 678354 50-mg treatment group and pooled placebo in FAS

ISIS 678354-CS3

If the comparison of the first secondary endpoint is statistically significant (p < 0.05), then the second secondary endpoint will be tested. However, if the comparison of the first secondary endpoint is not statistically significant, then all endpoints of lower rank will be considered exploratory. This process is repeated with each subsequent secondary endpoint.

4.9.1.4. Interim Analyses

There is no interim analysis planned for the study.

4.9.1.5. Examination of Subgroups

To evaluate the consistency of analysis results in the primary endpoint over parameters such as demographic and baseline characteristics, exploratory subgroup analyses will be performed if supported by data. The subgroups include but not limited to:

- Gender: Male, Female
- Prior history of pancreatitis within 10 years prior to Screening: Yes vs. No
- Previous treatment with Volanesorsen: Yes vs. No
- Region: North America, Europe (including United Kingdom), United States
- Age: < 65 years, ≥ 65 years
- Race: White vs. non-White
- Ethnicity: Hispanic or Latino vs. Not Hispanic or Latino
- Diabetic status: No vs. Type I or Type II
- Baseline TG: < median vs. \ge median

4.9.2. Primary Efficacy Variable

The primary efficacy analysis will take place after the last patient has completed the Week 53/ET visit and the database has been locked, and will be based on the percent change from Baseline in fasting TG at primary analysis time point.

The primary endpoint is the percentage change in fasting TG from Baseline to the primary analysis time point. The primary analysis of the primary endpoint is to compare the percent change from Baseline to the primary analysis time point in fasting TG between each ISIS 678354 treatment group (ISIS 678354 80 mg, ISIS 678354 50 mg) vs. pooled placebo using an ANCOVA model in the FAS. The ANCOVA model will use precent change from Baseline to the primary analysis time point in fasting TG as dependent variable, the two randomization stratification factors, prior history of pancreatitis within 10 years prior to Screening (yes vs. no), previous treatment with Volanesorsen (yes vs. no) and treatment group (ISIS 678354 80 mg, ISIS 678354 50 mg) as the fixed effects and nature log-transformed baseline fasting TG as a covariate. To account for potential heterogeneity in variance, the 95% CIs will be calculated using the robust variance estimator based on the Bell and McCaffrey method (Imbens & Kolesár 2016).

If patients have intercurrent event(s) before Week 23, e.g., treatment discontinuation, use of additional medication, changes in background or concomitant treatments, the Treatment Policy strategy will be implemented, the patients' assessments post intercurrent events will continue to be collected. All assessments including those post the intercurrent events will be utilized in the analysis.

Patients with missing TG value at the baseline and/or primary analysis time point will have fasting TG value multiply imputed using the multiple imputation methods described in Section 4.9.1.2 in the SAP. The are provided in the table below:

Treatments	ISIS 678354 80 mg Pooled placebo
Participant Population	Patients with FCS as defined by protocol eligibility criteria
Variable	Percent change from Baseline to primary analysis time point (average of Weeks 23, 25 and 27) in fasting TG
Intercurrent events (ICEs) and strategies	Discontinuation of study treatment prior to Week 23 Treatment policy strategy Disallowed concomitant therapy/procedure prior to Week 23 Treatment policy strategy
Population-level summary	Difference in means between ISIS 678354 80 mg and pooled placebo in the FAS
Description of estimand	The difference in means for percent change from Baseline to the primary analysis time point in fasting TG between ISIS 678354 80 mg and pooled placebo (regardless of early treatment discontinuation, use of additional medication, or change in background or concomitant treatments) in patients with FCS

Treatments	ISIS 678354 50 mg Pooled placebo
Participant Population	Patients with FCS as defined by protocol eligibility criteria
Variable	Percent change from Baseline to primary analysis time point (average of Weeks 23, 25 and 27) in fasting TG
Intercurrent events (ICEs) and strategies	Discontinuation of study treatment prior to Week 23 Treatment policy strategy Disallowed concomitant therapy/procedure prior to Week 23 Treatment policy strategy
Population-level summary	Difference in means between ISIS 678354 50 mg and pooled placebo in the FAS
Description of estimand	The difference in means for percent change from Baseline to the primary analysis time point in fasting TG between ISIS 678354 50 mg and pooled placebo (regardless of early treatment discontinuation, use of additional medication, or change in background or concomitant treatments) in patients with FCS

ISIS 678354-CS3

Statistical Analysis Plan

The sample SAS code for the ANCOVA model can be found below:

```
* Note:
*
  baseline = baseline TG
*
   impute = the iteration number in the multiple imputation
*
   TRTN = Treatment group: 0=Placebo, 1= ISIS 678354 50 mg, 2 = ISIS 678354 80 mg
*
   PANCR = Prior history of pancreatitis within 10 years prior to Screening: 0 = No, 1 =
Yes
*
   VOLAN= Previous treatment with Volanesorsen: 0= No, 1= Yes
*
   BM stderr= Bell and McCaffrev standard error
                       *****
****
        data TG; set TG;
           LOGBASE = LOG(baseline); /* log transformed baseline*/
        proc mixed data = TG;
          by _impute;
           class TRTN PANCR VOLAN;
           model PCHG = TRTN PANCR VOLAN LOGBASE;
           lsmeans TRTN/e diff cl;
           estimate 'ISIS 678354 50 mg vs Placebo' TRTN -1 1 0;
           estimate 'ISIS 678354 80 mg vs Placebo' TRTN -1 0 1;
        run;
```

The estimates from the fitted models for each of the 100 imputed datasets will be combined to provide an overall estimate with corresponding confidence intervals and p-value (Little & Rubin 2002). The following pseudo SAS code will be used to estimate corresponding confidence intervals and p-value:

```
proc mianalyze data=diff;
    modeleffects estimate;
    stderr BM_stderr;
run;
```

The following sensitivity analyses of the primary endpoint will be conducted to assess the robustness of the primary analysis result.

Sensitivity Analysis 1: PPS

The primary efficacy analysis with ANCOVA model for percent change in fasting TG from Baseline to the primary analysis time point described above will be repeated in the PPS.

Sensitivity Analysis 2: Completer Set (Subset of FAS)

The primary efficacy analysis with ANCOVA model for percent change in fasting TG from Baseline to the primary analysis time point will be repeated in the subset of the patients in the FAS with no missing TG values at the primary analysis time point.

Sensitivity Analysis 3: Exploring the robustness of the primary analysis (FAS)

Additional sensitivity analyses using different imputation approach with ANCOVA model will be conducted in the FAS to assess the robustness of the primary analysis results.

- 1. Patients with missing TG value at the primary analysis time point will be imputed using a pattern mixture model. Specifically, for patients treated with ISIS 678354 who discontinue the treatment due to AE or lack of efficacy (i.e., informative missing), their missing fasting TG data after the last dosing date will be multiply imputed using the copy increment from reference (CIR) approach based on the estimates from of the placebo patients. The CIR approach is detailed in (Carpenter *et al.* 2013). The assumption is when a patient discontinues treatment due to informative missing, from withdrawal onwards he/she would progress in the same way as the patients in the placebo group. For patients who discontinue due to other reasons and all patients from the placebo group, their missing data will be treated as non-informative missing, and data will be multiply imputed based on the distribution of their own treatment group.
- 2. All patients treated with ISIS 678354 will have missing TG values after the last dosing date multiply using the CIR approach based on the estimates from the placebo patients. Missing TG values for placebo patients will be imputed based on the distribution of the placebo group.

Sensitivity Analysis 4: Non-parametric analysis with Wilcoxon rank-sum test (FAS)

A nonparametric Wilcoxon rank-sum test will be performed on the percent change in fasting TG from baseline to the primary analysis timepoint in the FAS. Missing data will be handled using the same multiple imputation method as the primary analysis. The estimates for each of the 100 imputed datasets will be combined to provide an overall Hodges-Lehmann estimator of the location shift and corresponding 95% CI between each ISIS 678354 treatment groups group and the pooled placebo group.

Sensitivity Analysis 5: Tipping point analysis (FAS)

An additional sensitivity analysis using the 2-dimensional tipping-point approach will be conducted in the FAS to assess the impact of missing data on the result of the primary analysis.

The sensitivity analysis will be conducted as follows using the imputed data based on the primary imputation approach as described in Section 4.9.1.2 in the SAP:

- 1. For the placebo group, a positive constant shift (δ_c) will be added to or subtracted from percent change of the imputed TG values at the primary time point. The shift will be gradually increased
- 2. For each value of the placebo shift parameter, a positive constant shift (δ_t) will be added to or subtracted from percent change of the imputed TG values at the primary time point in the active treatment groups. The shift will be increased in a repeated process until the treatment effect is no longer significant at 0.05 level in step 5 below.
- 3. For each of the 100 imputed datasets, the same ANCOVA model as described for the primary analysis of the primary endpoint will be fitted to estimate treatment differences and standard errors.
- 4. The 100 sets of estimates will be combined with SAS PROC MIANALYZE as described in Section 4.9.1.2 in the SAP
- 5. Steps 1 to 4 will be repeated with different values of the shift parameters until the tipping points are reached.

Values of δ_c and δ_t will be determined post-hoc in order to define reasonable increments.

Sensitivity Analysis 6: ANCOVA model using log-transformed data (FAS)

The percent change from Baseline to the primary analysis time point in fasting TG between each ISIS 678354 treatment group (ISIS 678354 80 mg, ISIS 678354 50 mg) vs. pooled placebo will be compared using ANCOVA model with $\log(y/x)$ as dependent variable, where y is the value of fasting TG at primary analysis time point, x is the baseline value of fasting TG; and the two randomization stratification factors and treatment group as factors and nature log-transformed baseline fasting TG as a covariate. The model will provide an estimate of log post-baseline to baseline ratio for each treatment group as well as the ratios relative to the pooled placebo group and the corresponding 95% confidence intervals (CIs). The log post-baseline to baseline ratios will be converted back to the original ratio scale. The percent change from baseline for each treatment group will then be calculated based on the estimated ratio as 100% * (ratio -1). Similarly, the estimated upper and lower CIs for the ratio can be calculated as 100% * (CI - 1). Patients with missing fasting TG value at the baseline and/or primary analysis time point will have TG value multiply imputed using the multiple imputation methods described in Section 4.9.1.2 in the SAP.

Descriptive statistics and other data presentation

Descriptive statistics and cumulative distribution curves will be provided for observed fasting TG levels and percent change in fasting TG in each treatment group for the primary endpoint.

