- During the treatment, blood samples were collected every 4 weeks to check for the levels of triglycerides in the blood.
- Participants also completed questionnaires to check their own state and symptoms of the disease. They recorded any medical problems they had during the treatment.
- The treatment period lasted for 52 weeks (1 year).

Follow-up Period

- After ending their treatment, participants entered a 13-week follow-up period or an extension study if they completed the entire year of treatment.
- The extension study allowed researchers to collect more information on the safety and effectiveness of olezarsen.
- Those participants who did not move onto the extension study were followed up every 4 weeks of the 13-week follow-up period to check the safety and effectiveness of olezarsen.

Participants had check-up visits at the study clinic, both during treatment and for up to 13 weeks after treatment. Researchers observed participants' health and checked for any side effects.

What were the results of the study?

The results below include all 66 participants who received at least 1 dose of olezarsen or placebo.

How did the triglyceride levels change after 6 months of treatment in participants who took olezarsen compared to those who took placebo?

Researchers wanted to compare the change in fasted triglyceride levels from the start of the study between the olezarsen and placebo groups.

After 6 months:

- The triglyceride levels in the participants who received 80 mg of olezarsen decreased by 44% compared with placebo.
- The triglyceride levels in the participants who received 50 mg of olezarsen decreased by 22% compared with placebo.

Researchers considered the change in the participants who received 80 mg of olezarsen to be meaningful. Results in the group of participants that received 80 mg of olezarsen every 4 weeks had a reduction in triglyceride levels that were statistically significant from placebo. Statistical significance means that the numbers are reliably different, greatly aiding in data analysis. The participants who received 50 mg of olezarsen every 4 weeks had a reduction in triglyceride levels, but compared with placebo, was not statistically significant.

How did the occurrence of pancreatitis change after 1 year of treatment in participants who took olezarsen compared to those who took placebo?

Researchers wanted to compare the occrence of pancreatitis from the start of the study between the olezarsen and placebo groups.

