4.9.1.2. Handling of Dropouts or Missing Data

If there is missing TG data at baseline and primary analysis time point, a two-stage multiple imputation approach will be utilized.

First, patients with a missing fasting TG at the baseline will have missing values multiply imputed based on the observed baseline assessments from other patients. The Markov Chain Monte Carlo (MCMC) method will be used to impute the missing values. The imputation model will include baseline fasting TG value and 2 stratification factors (history of pancreatitis and previous treatment with Volanesorsen) (Schafer 1997; 1999). The TG values will be natural log-transformed before the imputation process, then back transformed after imputation to create the imputed data set. The SAS procedure PROC MI will be used to create 100 imputed datasets.

The following pseudo SAS code and seed (2438291) will be used to perform the multiple imputation for missing TG at baseline:

```
proc mi data = TG seed = 2438291 nimpute = 100 out=TG2;
transform log(baseline);
Mcmc;
var PANCR Volan baseline;
```

run;

The imputed baseline values will be merged with the observed post-baseline data and used for the second stage of imputation.

In the second stage of imputation, patients with a missing fasting TG at the primary analysis time point will have missing values multiply imputed based on the known assessments from the retrieved dropouts (patients who discontinue treatment before Week 23 but still have TG assessments at Weeks 23, 25, or 27), if there are a sufficient number of retrieved dropouts. The imputation model will contain the following variables: baseline fasting TG value, fasting TG values at post-baseline visits and 2 stratification factors (history of pancreatitis and previous treatment with volanesorsen), and the multiple imputation will be stratified by treatment group.

If there is no sufficient number of retrieved dropouts, missing TG value at the primary analysis time point will be imputed using a "wash-out" multiple imputation approach (Jump to Reference, J2R). With the approach, patients treated with ISIS 678354 will have missing TG values after the last dosing date multiply imputed based on baseline fasting TG, the 2 stratification factors of their own treatment group, and the imputation model for the placebo group. Patients in the placebo group will have missing TG values at post-baseline visits and the 2 stratification factors from the placebo group.

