The "wash-out" multiple imputation will be preformed in the following steps:

1. The Markov Chain Monte Carlo (MCMC) method will be used under the multivariate normality assumption to impute all missing values by treatment group. The variable list for imputations will include the baseline value, as well as all available post-baseline value, and stratification factors. To conform to the multivariate normality assumption, baseline, and post-baseline fasting lipid data will be natural log-transformed before the imputation process, and the variable values will be back transformed to create the imputed data set. The SAS procedure PROC MI will be used in the multiple imputation. The MCMC method will impute primary analysis time point data for each of the 100 datasets from the first imputation stage. EM algorithm will be used to derive a set of initial parameter estimates for MCMC method. A non-informative prior (Jeffreys' prior) will be used to derive the posterior distribution of the parameters. A total of 100 imputed datasets will be created from the above 2-stage multiple imputation process.

The following pseudo SAS code and seed (2438291) will be used to perform the multiple imputation for each treatment group:

```
proc mi data = TG2 seed = 2438291 nimpute = 1;
transform log(baseline) log(week5) log(week9) log(month3)
log(week21) log(month6) log(week29) log(week37) log(week45)
Log(month12);
mcmc;
var PANCR Volan baseline week5 week9 month3 week21 month6
week29 week37 week45 month12;
by _imputation_;
```

run;

If there is no missing data at baseline, then the baseline imputation will not be performed. The second stage of imputation will be performed to create 100 imputed datasets.

- 2. A general linear model will be fitted using the data in the placebo group for each imputed dataset
- 3. For patients in both ISIS 678354 dose groups, the imputed values after last dose date will be replaced with the values imputed using J2R method (calculated using the patients' own baseline fasting TG, the 2 stratification factors, and the model from step 2)
- 4. The variable values will be back transformed from nature log scale to the original scale in the final imputed datasets.

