For each of the 100 imputed datasets, the endpoint will be compared between ISIS 678354 treatment groups and pooled placebo using an ANCOVA model for continuous endpoints or logistic regression for binary endpoints as described in the primary analysis for each endpoint. The estimates from the 100 fitted models will be combined to provide an overall estimate with corresponding confidence intervals and p-value (Little & Rubin 2002)

The following pseudo SAS code will be used to estimate corresponding confidence intervals and p-value:

```
proc mianalyze data=diff;
    modeleffects estimate;
    stderr stderr;
```

run;

For the continuous endpoints, the treatment difference and the corresponding 95% CI will be presented. For the analyses using logistic regression, the odds ratio and the corresponding 95% CI will be presented.

Missing values at Months 3 and 12 and other lipid parameters will be imputed in a similar way to the primary analysis time point.

Only observed lipid data will be displayed in the data listings.

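### The SAP's pooling step states no complete-data degrees of freedom; run as displayed it uses a multiplier of about 1.96 instead of 2.02-2.03, a small excess in type I error when little is imputed

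*Combined protocol and SAP*

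**What the plan says.** SAP 4.9.2 fits an ANCOVA to percent change in fasting TG with treatment (three groups), the two stratification factors and log baseline TG. On the variance it says: "To account for potential heterogeneity in variance, the 95% CIs will be calculated using the robust variance estimator" of Bell and McCaffrey, with a citation. Protocol 10.6.3.1 says the same.

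The 100 sets of estimates are then combined. The SAP says "The following pseudo SAS code will be used to estimate corresponding confidence intervals and p-value", and the call that follows has two working lines: the estimate, and "stderr BM_stderr". SAP 4.9.1.2 introduces its own call with the same sentence and passes "stderr stderr". Neither call has an EDF= option. Neither section, nor protocol 10.6.3.1, says which df enters the pooling.

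There are two imputation routes. The first imputes within treatment group from retrieved dropouts. The fallback is jump-to-reference (J2R): "If there is no sufficient number of retrieved dropouts, missing TG value at the primary analysis time point will be imputed" from the placebo model. In the fallback's third step, for the active arms only, "the imputed values after last dose date will be replaced with the values imputed using J2R method". The protocol expects a low rate of missing data and gives no figure.

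**The concern.** The plan chooses a small-sample variance estimator because it expects unequal variances in arms of about 20. That estimator comes with its own df, well below the residual df. If the df is not carried into the pooling, half of the small-sample correction is lost: the robust standard error is referred to what is in effect a normal distribution.

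The pooled p-value decides both primary tests at two-sided 0.05. It also decides entry to the ranked secondary tests: "Testing of secondary endpoint family will be performed only if the comparison of the primary endpoint is statistically significant" for both doses. Fourteen of the 28 ranked tests (1-3, 5-9, 11, 12, 18, 19, 22 and 23) use the same ANCOVA and the same pooling. The tipping-point analyses also pool this way and look for the shift at which significance at 0.05 is lost, so their tipping points depend on the multiplier even when the primary p-value is far from 0.05.

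As the text stands, two programmers could both follow the SAP and report different intervals and p-values.

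**Working it through.** **Inputs from the documents.** Two-sided alpha 0.05 (SAP 4.9.1.3); m = 100 imputations (SAP 4.9.1.2); SD of percent change 46 (SAP 4.12); planned groups of 20/20/20, from 60 patients randomised 1:1 to cohorts and 2:1 within each; actual groups of 23 placebo, 21 on 50 mg and 22 on 80 mg (lay summary); six model parameters, so residual df 60 - 6 = 54 or 66 - 6 = 60; at least 65% with pancreatitis history, from the 35% cap in protocol 5.1.

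**The plan's own figure.** With 14 per group, difference 60 and SD 46, the noncentrality is 60/(46 × √(2/14)) = 3.45, and the t-test on 26 df has power 91.3%. The stated 90% is reproduced.

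**Step 1: df as displayed.** Without EDF=, the df is (m - 1)(1 + 1/r)², where r is the relative increase in variance due to missing data.

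| r | df | multiplier |
|---|---|---|
| 0.01 | 99 × 101² = 1,009,899 | 1.960 |
| 0.05 | 99 × 21² = 43,659 | 1.960 |
| 0.10 | 99 × 11² = 11,979 | 1.960 |
| 0.20 | 99 × 6² = 3,564 | 1.961 |

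Sample size does not appear in the formula.

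**Step 2: df that belongs to the standard error.** The Bell-McCaffrey df was computed for this ANCOVA over assumed shares of pancreatitis history (65-90%) and prior volanesorsen (10-50%) and two baseline shapes. The mean is 33.4-34.1 at 20/20/20 and 37.1-38.7 at 23/21/22. With randomisation in stratified blocks it is 34.9-35.1 (N = 60) and 38.9-39.1 (N = 66). The multiplier is 2.032 at 34 df and 2.023 at 39 df. Residual df of 54-60 would give 2.005-2.000.

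**Step 3: interval width.** For complete data, 1 - 1.960/2.032 = 3.6% and 1 - 1.960/2.023 = 3.1%. With imputation the Barnard-Rubin rule lowers the df further. At r = 0.05 and complete-data df 38, the observed-data df is (1/1.05) × 38 × 39/41 = 34.4. Combined with 43,659 it stays at 34.4, the multiplier is 2.031, and the shortfall is 3.5%. With 3 or 6 of 66 values imputed, simulation gives 3.5-3.9%.

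**Step 4: simulated type I error under the null**, as displayed and with the Bell-McCaffrey df:

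| Setting | As displayed | With the df |
|---|---|---|
| Complete data, equal variances | 5.5-5.8% | 4.8-4.9% |
| Complete data, all normal-data scenarios, 23/21/22 | 5.4-5.9% | 4.7-5.2% |
| Complete data, all normal-data scenarios, 20 per arm | 5.6-6.5% | 4.7-5.5% |
| Within-arm, 2-5% missing | 4.8-5.7%, mostly 5.2-5.7% | 3.9-4.9% |
| Within-arm, 10% missing | 4.3-5.3% | 3.5-4.4% |
| Within-arm, 15% missing | 3.1-5.1% | 2.5-4.4% |
| J2R, 2% missing | 4.8-5.3% | 4.0-4.4% |
| J2R, 5% missing | 3.7-4.2% | 3.0-3.6% |
| J2R, 15% missing | 1.8-2.3% | 1.4-1.8% |

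Monte Carlo standard error is about 0.2-0.3 points. In a further J2R set with 3 of 66 values missing, equal SDs gave 4.5-4.8% as displayed. The rate passed 5% (5.1-5.4%) only when placebo was the least variable arm.

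**Step 5: which p-values could move.** A statistic between 1.960 and 2.023-2.034 is significant only with the smaller multiplier. On the normal scale that is p from about 0.042 or 0.043 up to 0.05.

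**Step 6: the reported results.** The lay summary says the 50 mg group "had a reduction in triglyceride levels, but compared with placebo, was not statistically significant". A larger multiplier cannot reverse that, and by SAP 4.9.1.3 it closes the secondary family. For 80 mg, taking the reported 44% as a difference in points with the planning SD, 44/(46 × √(1/22 + 1/23)) = 44/13.72 = 3.21 (p = 0.001 as z, 0.003 on 38 df). An SD of about 73-75 would be needed to bring it into the window.

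**The case against.** - **The code is labelled sample and pseudo code.** True. Nothing displayed creates `BM_stderr`, and taken literally the call would pool the two dose contrasts together. A programmer must fill those gaps and might well add the df too. A reader might infer that the plan has chosen a normal multiplier; the documents do not support that. What they establish is that the df is unspecified, while the SAP says the displayed step produces the intervals and p-values. The citation of the variance method does not say which df enters Rubin pooling.
- **With no missing data there is nothing to pool.** Correct: SAP 4.9.1.2 imputes only if TG values are missing. The complete-data rows stand for the limit of one or two imputed values.
- **J2R is the likelier route and is already conservative.** This largely stands. With few dropouts there may not be enough retrieved dropouts for the within-arm route, and under J2R the correction usually moves a test already at or below 5% further down. The plan does not fix the route in advance, however, and its third step replaces only active-arm values after the last dose, so a real run would lie between the two sets of figures. J2R's conservatism is also a separate property and not a reason to leave the df open.
- **The remedy is partly a choice.** Residual df would already give 2.00 and about 5.1-5.2% with complete data. The Bell-McCaffrey df is preferred because it belongs to the standard error that the SAP names.

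**Conclusion.** The omission is real and minor. Conditional on running the call as displayed, the multiplier is about 1.96 instead of 2.02-2.03, intervals are about 3-4% too narrow, and type I error is about 5.5-6% when very little is imputed, against about 5% with the df. Some scenarios with larger placebo variance, skewed data or 20 per arm reach 6.5%.

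Two stronger readings are not supported. One is that within-arm imputation inflates the error in general: the excess is confined to about 2-5% missing and disappears at 10-15%. The other is that a reported conclusion is in doubt: 50 mg was not significant, the secondary family was therefore closed, and 80 mg lies well outside the window at the planning SD. The observed SD is not in the documents, so the 80 mg statement is an approximation.

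The Rubin df and the multipliers follow by formula once the df is known. The error rates rest on assumptions that the documents do not give: stratum shares, baseline shape, missing counts, SD patterns by arm and a simplified imputation model.

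**What to change.** Add to SAP 4.9.1.2 and 4.9.2: for each imputed dataset and each dose-versus-placebo contrast, the Bell-McCaffrey df is output with `BM_stderr`; each contrast is pooled separately; and the mean df over the imputations is supplied as the complete-data df through EDF= (Barnard-Rubin). Show the option in both pooling calls. Apply it to the primary endpoint, to the continuous secondary endpoints analysed by the same ANCOVA, and to the tipping-point analyses of those endpoints. The logistic endpoints are not affected.

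The cost is a sentence in each section and modest programming (output of the df and pooling by contrast). Intervals become about 3-4% wider. Under J2R with equal SDs the 80 mg test becomes slightly more conservative: 4.5% to 3.8% with 3 values missing, and 3.5% to 2.7% with 6.
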